4.3 Secondary Objectives (if applicable)

To measure myoelectric signals with the G-Tech WPS and determine if there are differences in signal patterns for right colon resections, left colon resections, and rectal resections.

5 Study Design

5.1 General Design Description

Single-arm, nonrandomized feasibility study to evaluate the ability to correlate myoelectric signals of the abdomen after surgery to GI functional recovery.

5.1.1 Study Date Range and Duration

Data Collection: June 1, 2022 to May 30, 2023

Data Analysis: June 1, 2022 to May 30, 2024 (data analysis intentionally overlaps with collection as it is done algorithmically in near real-time)

5.1.2 Number of Study Sites

Single site. Yale New Haven Hospital

5.2 Outcome Variables

5.2.1 Primary Outcome Variables

GI functional recovery after surgery as measured by first flatus

5.2.2 Secondary and Exploratory Outcome Variables (if applicable)

- Rate of inpatient postoperative ileus
- Rate of readmission for post-discharge ileus
- GI functional recovery as measured by first bowel movement

5.3 Study Population

Patients undergoing resection of portions of the colon and rectum with anastomosis.

5.3.1 Number of Participants

200

5.3.2 Eligibility Criteria/Vulnerable Populations

Any subject who undergoes an open or laparoscopic colon or rectum resection surgery

Inclusion Criteria:

1. Willing and able to provide informed consent
2. Eighteen (18) years of age or older
3. Subject is willing and able to follow all study requirements
4. Subject has undergone or will undergo a laparoscopic or open colorectal surgery with resection and anastomosis

Exclusion Criteria:

[figure not shown]
1. Subject is pregnant or suspects pregnancy.
2. Known allergy to medical grade adhesive.

6 Methods

6.1 Treatment – Device

6.1.1 Intended Use for Device (provide the following information for each device being investigated in the study)

The G-Tech WIRELESS Patch System is a non-invasive wireless gastrointestinal monitoring system. The platform has received approval via the 510(k) process supervised by the U.S. Food and Drug Administration. The system consists of G-Tech Patches, the G-Tech Patch Monitor, an iOS application, and data analysis algorithms.

The G-Tech Patch acquires and transmits electrical signals from the gastrointestinal tract via Bluetooth to the G-Tech Patch Monitor. The G-Tech Patch Monitor receives the raw data and periodically uploads it to a secure cloud server. Additionally, the Patch Monitor has a patient interface to allow the patient to manual enter events such as meals, bowel movements, pain or the taking of medications.

Figure 1 The G-Tech Wireless Patch System (WPS)

Data analysis algorithms process the uploaded data to measure and report myoelectrical motor activity levels for the stomach and intestines. These measurements will be made available to the study investigators to identify correlations between return and patterns of myoelectrical activity with time to feeding and discharge. Patients do not have

[figure not shown]

Figure 2 The G-Tech Patch and G-Tech Patch Monitor App

independent access to either the raw data or calculated results except as shared with them by their physician.

6.1.2 Device Administration and Schedule

The G-Tech patches will be placed on patient post-operatively following surgery either in the Post Anesthesia Care Unit (PACU) or in their hospital room, within 4 hours of being transported out of the operating room. Research staff will activate three (3) G-Tech patches and pair them with the G-Tech App on an iPhone 7 (provided). The patches will be periodically sending the data to the paired iPhone 7, which will remain by the patient's bedside until discharge. The G-Tech Patches are intended to run continuously for up to 6 days and have been shown to run continuously for up to 14 days in pilot testing. The patient, caregiver or staff member shall record activities such as first solid meal, first flatus, first bowel movement on the easy-to-use iPhone app during the patients stay. The inpatient physician-led team will also remind the patient to enter information into the app daily. The recorded events and gut myoelectrical activity are transferred wirelessly via the paired iPhone to the cloud. The Patches shall be replaced as needed. All patches are removed before patient is discharged.

Skin Preparation

Locate the approximate patch locations on the abdomen according to Figure 2. Patch locations can be varied depending upon the surgery incisions. Patches are not sterile and should be placed at least an inch distance from any incision. Clip abdominal hair as needed in the patch location if not clipped prior to surgery. Clean the skin thoroughly using alcohol pads and let dry before applying the patches.

[figure not shown]

[figure not shown]
Figure 3 G-Tech Patch abdominal locations

G-Tech Patch Placement Procedure

Patches should be placed on the patient as soon as possible and in no case later than **4** hours after surgery. Staff member shall activate and apply G-Tech Patches (recommended number of patches is 3) to the patient in the locations shown in Figure 3. The G-Tech Patches are intended to run continuously for up to 6 days. Patches shall be replaced as needed. Patches are removed before patient is discharged.

Study subject instructions for reporting events such as diet and physical symptoms

The patient, caregiver or staff member shall record activities such as first solid meal, first flatus, first bowel movement on an easy-to-use iPhone app during the patient's stay. The recorded events and gut myoelectrical activity are transferred wirelessly via the paired iPhone to the cloud. If they forget to log an event, they may change the time to backlog.

*Figure 4 Logging events in the G-Tech App***6.1.3 Method of Assignment/Randomization (if applicable)**

n/a

6.1.4 Device Calibration

n/a

6.1.5 Storage Conditions

Each device comes sealed from the manufacturer and is designed to be used and re-processed. Sealed patches will be kept in a temperature-controlled (10-40 degrees Celsius), locked research cabinet in the PI's divisional offices. Used patches will be placed in a sealed plastic bag and returned to the manufacturer per their re-processing instructions. The re-processing itself has been reviewed and approved by the U.S. FDA under the manufacturer's 510(k) approval. The investigator and research team have no role in re-processing other than returning opened and activated patches back to the manufacturer through regular U.S. mail.

6.1.6 Concomitant therapy

No restrictions

6.1.7 Restrictions

No tub bathing while device is in use (showers ok).

The G-Tech Patch has an IP23 rating which means it is protected from touch by fingers and objects greater than 12 millimeters. The rating also indicates that it is protected from water spray less than 60 degrees from vertical. It is advised to take short 5-minute showers with back facing shower head. Tub bathing or any type of bathing where the device could be submersed in water or exposed to moisture or water or soaked with water (sponge bath or bed bath) during washing is not permitted.

6.2 Assessments**6.2.1 Efficacy**

n/a

6.2.2 Safety

The investigator will collect data and report the treatment or device related events that occur during the Study. Anticipated adverse events in this study are adverse events that are not considered serious and have previously been identified in the nature, severity, or the degree of incidence. An anticipated adverse event is synonymous with adverse event. These are not serious, and they are possibly, probably, or definitely related to the device.

Assessment for unanticipated adverse device effects and serious adverse events will take place at each treatment visit prior to, during, and after each treatment, and at each follow-up visit.

6.2.3 Adverse Events Definition and Reporting

Adverse Event Reporting Requirements

Adverse event data will be collected on the adverse event case report form for the study. Adverse events are not required to be reported immediately to G-Tech Medical. Adverse events are to be collected, and data is to be provided on the case report form.

Assessing for Adverse Events

Assessment for adverse events will take place during the wearing of the G-Tech Patch device. List of Anticipated adverse events related to the G-Tech Patch:

- Erythema
- Pruritis (itching)
- Ecchymosis (bruising)
- Rash
- Discomfort

Unanticipated Adverse Device Effect

Unanticipated Adverse Device Effect Definition (UADEs)

An unanticipated adverse device effect (UADE) is defined as “any serious adverse effect on health or safety or any life-threatening problem or death caused by, or associated with, a device, if that effect, problem, or death was not previously identified in the nature, severity, or degree of incidence in the investigational plan or application (including a supplementary plan or application), or any other unanticipated serious problem associated with a device that relates to the rights, safety, or welfare of subjects”.

UADE Reporting Requirements (21 CFR 812.46 & 812.150)

UADEs must be reported by the clinical investigator to the reviewing IRB and G-Tech Medical, as described below:¹

- An investigator shall notify G-Tech Medical immediately but no later than within 24 hours first notification of a UADE.
- G-Tech Medical, with the assistance of the study site, must immediately conduct an evaluation of a UADE.
- G-Tech Medical must report the results of the evaluation to the reviewing IRB, and participating investigator within 10 working days after G-Tech Medical first receives notice of the effect (§§ 812.46(b), 812.150(b)(1)).
- Investigators are required to submit a report of a UADE to the reviewing IRB and G-Tech Medical as soon as possible, but in no event later than 10 working days after the investigator first learns of the event (§ 812.150(a)(1)).

Assessing for UADEs

Assessment for UADEs will take place at each treatment visit prior to, during, and after each treatment, and at each follow-up visit.

Serious Adverse Events (SAEs)

Serious Adverse Event Definition

Serious adverse events are anticipated and serious in nature. Serious adverse event is defined as follows:

- Results in death,
- Is life threatening,
- Requires inpatient hospitalization or prolongation of existing hospitalization,
- Results in persistent or significant disability/incapacity, or
- Is a congenital anomaly / birth defect

SAE Reporting Requirements

An investigator shall notify G-Tech Medical immediately but no later than within 24 hours of a SAE. G-Tech Medical shall conduct an immediate investigation of any SAE. An investigator shall submit to G-Tech Medical and to the reviewing IRB a report of any SAE occurring during an investigation as soon as possible, but in no event later than 10 working days after the investigator learns of the effect.

Assessing for SAEs

Assessment for SAEs will take place at each treatment visit prior to, during, and after each treatment, and at each follow-up visit.

Categories of Device Relationship

The following categories will be used to document adverse events and serious adverse events relatedness to the investigational device or treatment, and what is reportable to G-Tech Medical.

ATTRIBUTION	DEFINITION	DATA COLLECTED
Unrelated	The adverse event is clearly not related to the device or procedure(s). This is NOT collected.	NO
Possibly Related	The adverse event may be related to the device or treatment(s). This will be collected according to the reporting requirements in this protocol.	YES
Probably Related	The adverse event is likely related to the device or treatment (s). This will be collected according to the reporting requirements in this protocol.	YES
Definitely Related	The adverse event is clearly related to the device or treatment (s). This will be collected according to the reporting requirements in this protocol.	YES
Unknown	The investigator cannot determine the relatedness of the adverse event to the device. This will be collected according to the reporting requirements in this protocol.	YES

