6.3.1 Study Schedule

Preoperative period – Study Consent

Within 4 hours of existing operating room – Patches placed by study staff

Daily postoperative visit – reminder to enter information to the supplied iPhone

Day of discharge – Removal of patches by study staff

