6.3.6 End of Study and Follow-up

End of study will be discharge of the patient and removal of patches, or early withdrawal by patient or clinician request.

30-days after discharge each patient's electronic medical record will be reviewed for documentation of primary and secondary end points and entered into a REDCap database.

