6.4.3.3 Safety

Anticipated and unanticipated adverse device events will be monitor through hospitalization and 30-days after surgery based on the definitions above. Descriptive statistics will be reviewed with the study team and the manufacturer.

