1.4. Reason for Study Exit

Completed study visits as planned: if checked, skip to Principal Investigators' signature

Screen Failure: if yes State reason for screen failure

Voluntary subject withdrawal, e.g., no longer wanted to participate

Investigator decision to withdraw subject from the study

Other

Appendix 6

Adverse Event Form

A. DATE OF ADVERSE EVENT - ADVERSE EVENT # _____ OF _____			
1. Date of Adverse Event: (1 event per form)	____ / ____ / ____ Month Day Year		
2. Post-op Day:	 0  1  2  3  4  5  6  7  _____		
B. ADVERSE EVENT NOTED BY SITE			
COMPLETE THIS FORM FOR ALL ANTICIPATED, NOT SERIOUS, ADVERSE EVENTS			
1. Date of Adverse Event Onset	____ / ____ / ____ Month Day Year		
2. Date Adverse Event Reported to the Site	____ / ____ / ____ Month Day Year		
3. Date Adverse Event Reported to the IRB  N/A	____ / ____ / ____ Month Day Year		
C. ANTICIPATED ADVERSE EVENT (Check One per Form)			
#	ADVERSE EVENT TYPE	YES	ADVERSE EVENT # (Chronologically # by 1 st event to last event)
1.	Erythema		
2.	Itching (pruritis)		
3.	Ecchymosis		
4.	Rash		
5.	Discomfort		
6.	Allergy to adhesive		
7.	Other: _____ _____		

D. ANTICIPATED ADVERSE EVENT OUTCOME / ATTRIBUTION / TREATMENT			
OUTCOME (COMPLETE AT EACH VISIT UNTIL EVENT RESOLVED)			
1.	 Event resolved/ patient recovered – Enter date resolved below: 
 ____ / ____ / _____ Month Day Year 
		
	 Event ongoing / no current treatment  Event ongoing / still under treatment  Uncertain – subject lost to follow-up  Ongoing at end of study at time subject was terminated from study and MD is aware of this event at study closure.		
	ATTRIBUTION		
	2.	Relatedness	Definition
		 Unrelated	Clearly not related to the study device
 Possibly related		May be related to the study device	

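### Sections 6.2.2, 6.2.3 and 6.4.3.3 give conflicting safety windows, and no scheduled contact lists an adverse event or skin check

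*Combined protocol and SAP*

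**What the plan says.** Section 6.2.3 sets the timing for adverse events: "Assessment for adverse events will take place during the wearing of the G-Tech Patch device". Its list of anticipated events is erythema, itching, bruising, rash and discomfort.

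For the more serious categories the same section uses visits: "Assessment for UADEs will take place at each treatment visit prior to, during, and after each treatment, and at each follow-up visit", and likewise "Assessment for SAEs will take place at each treatment visit prior to, during, and after each treatment, and at each follow-up visit". Section 6.2.2 repeats this timing. It also says that the investigator collects device-related events occurring during the study.

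The schedule in 6.3.1 and 6.3.5 contains preoperative consent, patch placement, a 5-minute daily visit and a 5-minute removal on the day of discharge. The stated content of the daily visit is a "reminder to enter information to the supplied iPhone". Section 6.3.6 adds: "End of study will be discharge of the patient and removal of patches", or early withdrawal. It then provides for a record review 30 days after discharge, for the primary and secondary end points.

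The analysis section, 6.4.3.3, states: "Anticipated and unanticipated adverse device events will be monitor through hospitalization and 30-days after surgery based on the definitions above". Results are to be summarised descriptively. The Adverse Event Form in Appendix 6 heads its outcome block "OUTCOME (COMPLETE AT EACH VISIT UNTIL EVENT RESOLVED".

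**The concern.** A reader trying to carry out safety collection would find three timing rules and no contact at which any of them is put into practice. Three of the five anticipated events (erythema, bruising, rash) are visible skin changes, and skin under a patch can be inspected only when the patch is replaced or removed. Final removal falls on the day of discharge, which is also the end of study. The moment when covered skin is first seen is therefore usually the last scheduled contact, and nothing at that contact prompts staff to look or to record.

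Skin tolerability is among the device risks named in 3.2.1, and 6.4.3.3 will produce figures on it. Without a prompted check, a low or zero count cannot be told apart from not having looked. A summary described as reaching 30 days would in practice have no planned ascertainment of device events after discharge.

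**Working it through.** No calculation applies. The plan states no safety event rate, count or precision target. The check sets the passages side by side.

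**1. The windows.**
- 6.2.3, adverse events: while the patch is worn.
- 6.2.2 and 6.2.3, unanticipated device effects and serious events: at treatment visits and follow-up visits.
- 6.2.2 with 6.3.6, collection of device-related events: during the study, which ends at discharge with patch removal, or at early withdrawal.
- 6.4.3.3, anticipated and unanticipated device events: the hospital stay and up to 30 days from surgery.

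The first and last both cover anticipated device events and end at different times. The third also ends before the last whenever discharge comes before day 30.

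**2. The contacts.** The schedule has no visit called a treatment visit and no follow-up visit. The daily visit is described as an app reminder, and the discharge contact as removal of patches. Neither lists a skin or adverse event check. The record list in 7.7 does not name the Adverse Event Form, although it is Appendix 6.

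**3. After discharge.** Let L be the number of days from surgery to discharge.
- End of study: day L.
- End of the 6.4.3.3 window: day 30.
- Record review: day L + 30.
- Part of the 6.4.3.3 window with no scheduled contact: 30 − L days, for L below 30.

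Since L + 30 is never earlier than day 30, the review comes late enough to cover the window. The gap is in its content: it is confined to primary and secondary end points, and 5.2.1 and 5.2.2 contain no device-safety item. The telephone call in 6.4.5 is for missing data.

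**4. Three reactions followed through the plan.**
- Itching during wear: inside every stated window, and the patient can report it, although no contact prompts the question.
- Redness first seen as the patch is lifted: at the edge of the 6.2.3 window and inside that of 6.4.3.3. Staff are present and the form can hold it, but no step requires them to inspect or record. If it is recorded, Appendix 6 asks for the outcome at later visits, and none is scheduled.
- Mild rash at home after discharge: outside 6.2.3 and after end of study, but inside 6.4.3.3 up to day 30. No contact is planned, and the record review does not name it.

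**5. Size.** An estimate would need the reaction rate, the share of reactions first visible at removal, and the share of those that staff would leave unrecorded. The documents give none of the three, so no figure is offered.

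**The case against.** Much can be said for the plan. Section 6.4.3.3 covers the whole hospital stay, and patches come off before discharge, so removal lies inside that window. Section 6.2.2 collects device-related events during the study, and removal is part of how the study ends. The wearing-period sentence says when assessment happens; it does not tell staff to disregard what they then see. Appendix 6 has separate dates for onset and for report to the site, and an outcome option for events still ongoing when the study ends. Itching and discomfort can be reported during wear, patches may be replaced as needed, and placement, daily visit and removal can be read as before, during and after treatment. Safety is neither a primary nor a secondary outcome, and 7.12 rates the study as low risk.

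Most of this stands. A reader might infer that adverse events are sought solely during wear, that everything appearing at or after removal is lost, and that the reported rate is biased low by a calculable amount. The documents do not support that. Section 6.4.3.3 states a wider window, staff who remove the patches can see and record a reaction, and any numerical shortfall would need assumed rates and the discarding of every finding at removal.

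The objection does not remove the conflict between windows, the undefined visits, or the absence of any assigned check. Section 6.4.3.3 refers back to the definitions in 6.2 and adds no procedure of its own, so its 30-day claim is not backed by any planned activity after discharge.

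**Conclusion.** The point holds as a contradiction between sections combined with a gap in ascertainment. The safety windows must be reconciled. Reactions first visible at removal are at risk of under-recording, because nothing prompts the check. Mild reactions starting after discharge are unlikely to be captured, because no contact or record review is assigned to them. The direction of any error is towards too few recorded events; its size cannot be determined from the documents.

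The consequence is confined to the descriptive safety summary. The analyses of myoelectric activity against recovery are not affected. The conclusion assumes that the schedule in 6.3.1 and 6.3.5 is complete, that staff do what is written and no more, and that at least some skin reactions lie under the patch. If site practice already includes a skin check at removal, the in-hospital part reduces to writing that down, while the period after discharge still needs a decision. The correction should be made: it is cheap, and 6.4.3.3 as worded claims more follow-up than the plan provides.

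**What to change.** 1. State one safety window, in the same words, in 6.2.2, 6.2.3 and 6.4.3.3, and say explicitly that findings at patch removal count.
2. Replace the undefined treatment and follow-up visits with the contacts that exist: placement, daily visit, patch replacement, and removal at discharge. Add the adverse event check to 6.3.1 and 6.3.5.
3. At each replacement and at removal, record patch-site reaction yes/no on Appendix 6, so that absence of a reaction is a recorded observation. Add the form to the list in 7.7.
4. For the period after discharge, choose one of two options. Either add device-related adverse events to the 30-day record review in 6.3.6, with a telephone call only for patients whose event is open at discharge, or limit the claim in 6.4.3.3 to the hospital stay. Under the first option the report should say that new reactions after discharge are found only if they reached the medical record.

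The cost is protocol wording, a few form fields, about a minute at visits already planned, and a small number of calls. The reported reaction rate may come out somewhat higher.

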6.2.4 Pharmacokinetics (if applicable)

n/a

6.2.5 Biomarkers (if applicable)

n/a

6.3 Study Procedures

If a patient is unreachable by telephone, an alternative recruitment strategy will be used where they are approached in person in the preoperative readiness area prior to proceeding to the OR. The same scripted paragraph will be read, and they will be offered the opportunity to e-consent using the REDCap form provided on a study-supplied, secured iPad.

